Clinical evaluations: Physical exam, ECOG status, and weight will be collected pre-dose on dosing days. Medical and surgical history, height and neuropathy assessment (for MM subjects only) need only be collected at the screening visit. Prior to dosing on day 1 of every cycle, BSA must be calculated.
ECG: ECGs will be performed at the timepoints in the SOA as follows: Screening ECGs: Single ECG Baseline (pre-dose cycle 1 day 1): Three baseline ECGs will be collected approximately 15 minutes apart (\pm 5 minutes), with each baseline ECG in triplicate run consecutively (ie, all 3 ECGs should be completed within a total of 5 minutes from the start of the first to the completion of the third) for a total of 9 ECGs Cycles 1 through 4: Triplicate ECGs run consecutively (ie, all 3 ECGs should be started with \pm 5 minutes of infusion and be completed within a total of 5 minutes from the start of the first to the completion of the third) Cycle 5 and all subsequent cycles: Single ECG For Part 4 Cohorts 5a and 5b as well as Part 5A, 12-lead ECG assessments for C1D4 through D7 are optional based on investigator discretion.
ECHO or MUGA: Additional ECHO/MUGA, cardiac imaging and cardiac assessments are to be conducted if any clinical signs or symptoms of cardiomyopathy or other cardiac compromise are noted. If an ECHO or MUGA was performed within 4 weeks of C1D1 as part of standard of care, then it does not have to be repeated during screening as long as the same modality is used throughout the study. During LTFU and ECHO/MUGA is only required at the first LTFU visit.
Hospitalization for TLS monitoring and prophylaxis: All subjects will be hospitalized to monitor for TLS. Hospitalization will begin within 24 hours before the first dose of AMG 176 and continue until 24 hours post first AMG 176 dose for subjects on the AMG 176 QW schedule (Parts 1b, 3b, and 4) or post second dose of AMG 176 for subjects on the BIW schedule (Parts 1a and 3a). Hospitalization period can be increased per institutional standards or investigators discretion.
TLS Prophylaxis: See Section 6.1.4.1 for prophylaxis requirements including additional serum chemistry and hematology laboratory samples that must be collected within 24 hours prior to the first dose, and electrolyte values must be within normal range prior to AMG 176 dosing. Hospitalization for the purpose of TLS prophylaxis will not be captured as a Serious Adverse Event (SAE).

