2.3.2.1 Tumor Lysis Syndrome

Administration of AMG 176 has been associated with TLS including 1 subject with a fatal outcome out of 109 safety-evaluable subjects. The BCL2 inhibitor venetoclax also carries an associated risk of TLS, suggesting this may represent a feature of antiapoptotic therapy. Subjects with a high tumor burden or compromised renal function (eg, ISS Stage II/III) may be at elevated risk for TLS, which may further increase in the setting of combinational therapy with azacitidine due to the anticipated increase in

antileukemic activity. To mitigate the risk of TLS, blood chemistry (potassium, uric acid, phosphorus, calcium, and creatinine) must be assessed in all subjects and any pre-existing abnormalities must be corrected prior to starting treatment with AMG 176. In addition, subjects must be appropriately hydrated prior to each dose of AMG 176. Refer to Section 11.9 for specific recommendations regarding the mitigation and management of TLS.

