Part 3b (AML) will include weekly doses of AMG 176 monotherapy at 120, 180, and 240 mg/m² to inform the combinational therapy cohorts in Parts 4 and 5. Clinical trial results from Part 1a and Part 1b demonstrated that dose levels of AMG 176 of less than or equal to 240 mg/m² (Part 1a BIW; Part 1b QW) were not associated with increased troponin in contrast to the 360 mg/m² dose level where 2 of 8 subjects experienced a DLT (troponin elevation). Additionally, clinical responses in AML were observed at doses \leq 240 mg/m². To avoid the potential for cardiac toxicity with the MTD of 360 mg/m², only doses \leq 240 mg/m² will be further investigated on this study, with this dose representing the monotherapy RP2D. Additionally, preclinical data demonstrates that MCL1 inhibition is more efficacious in combination with other antileukemic therapies. Consequently, combinational therapy will be prioritized in this study to optimize the clinical benefit to subjects (Parts 4 and 5).

Part 4 will start with AMG 176 60 mg/m² in combination with azacitidine and will begin after completion of the 120 mg/m² AMG 176 monotherapy cohort in Part 3b. The decision to initiate enrollment in Part 4 will be made by the DLRT after the review of all available safety and tolerability data from the 120 mg/m² AMG 176 monotherapy cohort. Following Part 4 (combination dose exploration), a dose expansion phase (Part 5) will be conducted in approximately 68 subjects to confirm safety, PK, and PD at the MTCD and to obtain additional safety and efficacy data.

Additionally, dose levels lower than 30 mg/m² may also be explored if required or supported by emerging data. Intermediate doses and alternative dose frequencies may also be used if required or supported by emerging data. For each part, DLTs will be assessed during DLT evaluation period. See Section [6.2.1.2.2](#) for defined DLTs for MM and AML. Subjects who complete the DLT evaluation period (see Section [6.2.1.1](#)) without experiencing a DLT may proceed to a higher dose level within Part 3b or crossover to Part 4 combinational therapy for the following treatment cycle once the target cohort has been deemed safe by the DLRT and after consultation with the sponsor. Dose-limiting toxicities experienced by subjects who proceeded to a higher dose or combination treatment as described above will not be considered for dose level decisions. However, the DLRT will take this information into account to inform dose escalation recommendations.

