4.1.3 Drug-drug interaction Assessments with Itraconazole in the United States (Part 3d)

A separate cohort of about 11 subjects with AML will be enrolled for this DDI assessment using a fixed sequence design ([Figure 1-7](#)), where AMG 176 will be

co-administered with itraconazole during week 1 followed by dosing of AMG 176 alone in subsequent weeks. Since subjects are hospitalized during the first week of AMG 176 dosing, itraconazole administration will be limited to the first week to ensure proper monitoring and oversight of subjects in the event of increased exposure to AMG 176. A 7-day sentinel dosing will be utilized between the first and second subject enrolled in this cohort. All safety data available will be evaluated in the first subject prior to enrolling all subsequent subjects.

Subjects will receive:

- Oral itraconazole capsules (200 mg) QD starting at 8 am on day -3 through day 4 (total of 7 days) to achieve adequate CYP3A4 inhibition prior to, and following, AMG 176 administration.
- Intravenous AMG 176 (60 mg/m²) on day 1 at approximately the same time as itraconazole dosing (± 5 minutes).

Serial PK sampling will be conducted at specified time points after the AMG 176 dose on day 1 to characterize the plasma concentrations of AMG 176 when given in combination with itraconazole. Subjects will receive AMG 176 (60 mg/m²) alone on day 8 and day 15. Serial PK sampling will be conducted at specified time points after the AMG 176 dose on day 15 to characterize the plasma concentrations of AMG 176 without itraconazole. AMG 176 pharmacokinetics will be compared from day 1 (with itraconazole) relative to day 15 (without itraconazole). After day 15, subjects will be eligible to receive the highest cleared monotherapy or combination therapy dose if deemed safe by the investigator and Amgen medical monitor.

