6.1.4.1 Tumor Lysis Prophylaxis (All Subjects)

There is a potential for TLS in subjects affected by hematologic malignancies especially in those with bulky disease, elevated pretreatment lactate dehydrogenase (LDH) levels, elevated leukocyte count, renal dysfunction, and dehydration. To mitigate the risk of TLS, AMG 176 ramp-up dosing (see Section 6.1.1) will be used and TLS prophylaxis must be initiated in all subjects prior to all ramp-up dosing of AMG 176 and prior to all subsequent dose escalations (ie, first dose on the targeted cohort dose level). In Part 5B, subjects will receive ramp-up dosing on days 1 and 2 of week 1 in cycle 1 followed by the target dose starting on day 3. Prior to administering these doses, all electrolyte values (including potassium, uric acid, phosphorous, calcium, and creatinine) should be reviewed and must be within normal range. However, LDH is not mandatory.

All subjects will be hospitalized to monitor for TLS and all TLS monitoring assessments will be performed as outlined in the Schedule of Assessments (see Section 1.3).

The management recommendations below focus on the minimum initial responses required. If a diagnosis of TLS is established, ongoing intensive monitoring and

multi-disciplinary management will be conducted per institutional protocols (Coiffier et al, 2008; Cairo et al, 2004).

Tumor lysis syndrome prophylaxis includes:

- Allopurinol or equivalent should be used to reduce uric acid level. This should be initiated at least 72 hours prior to dosing. Treatment may need to be continued for up to 5 weeks. Other agents to reduce uric acid level, such as rasburicase, may be used per principal investigator discretion and the institutional guidelines. Dosing per institutional guidelines.
- NOTE: Allopurinol is unapproved for TLS prophylaxis in Japan.
- Hospitalization and monitoring, should begin the night before AMG 176 administration and must continue until at least 24 hours post-dose (QW schedule) or until 48 hours post the first dose in the BIW dosing schedule
- NOTE: Subjects in Part 3c will be hospitalized for a minimum of 29 days beginning from the night before AMG 176 administration in the first cycle.
- IV hydration must be started the night before AMG 176 administration and to be continued until at least 24 hours post-dose (QW schedule) during hospitalization as clinically tolerated (refer to Section 11.8.1 for more details about the level of IV hydration required)

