- Monitoring of electrolyte values is required prior to dosing anytime a dose is higher than one previously given to the subject. This will include at the following times:
 - Prior to the week 1, day 1 dose
 - Prior to each dose during the ramp-up period
 - Prior to the initial dosing at the target dose level
- Prior to administering these doses, all electrolyte values (including LDH, potassium, uric acid, phosphorus, calcium and creatinine) must be reviewed and within normal range (samples must be drawn within 24 hours prior to dosing of AMG 176). The investigator's decision to proceed with AMG 176 treatment initiation will be based on these laboratory values.

Within the first 24 hours after either the first dose or dose escalation, if any laboratory criteria for TLS are met, no additional AMG 176 doses should be administered until resolution. A rapidly rising serum potassium is a medical emergency.

Prophylactic dose reductions for potassium, phosphorus and/or uric acid values at the high end of normal range should be considered.

If the potassium, uric acid, inorganic phosphate and/or creatinine values are higher than the normal range or the calcium is lower or higher than the normal range, this (these) value(s) can be approved following a discussion between the Amgen medical monitor and investigator.

On the AMG 176 dosing days chemistry labs must be performed pre-dose (within 4 hours before AMG 176 administration), 2, 4, 8, 12 and 24 hours after the start of AMG 176 infusion. Pre-dose labs will be used as baseline to assess potential

electrolytes abnormalities occurring post AMG 176 administration. These labs must be reviewed in real time by the investigator.

Day 2 dosing of AMG 176 (BIW schedule) should not be administered until the 24 hours post dose laboratory values are reviewed by the investigator.

All 24-hour laboratory assessments may be taken \pm 2 hours, if necessary.

Monitor for signs and symptoms of TLS (eg, fever, chills, tachycardia, nausea, vomiting, diarrhea, diaphoresis, hypotension, muscle aches, weakness, paresthesias, mental status changes, confusion, and seizures). If any clinical features are observed, recheck potassium, phosphorus, uric acid, calcium and creatinine within 1 hour.

Additional information on the management recommendations of laboratory abnormalities can be found in Section [11.2](#).

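### The Table 1-9 note ends TLS hospitalization after the first dose or doses, but the body text calls for it again at the target dose, and the cycle 2+ schedule has no TLS rows for escalation or crossover

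*Protocol*

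**What the plan says.** **The note.** Protocol Section 1.3, Table 1-9, says that all subjects are hospitalized for TLS monitoring. It then fixes the stay: admission falls in the day before the first dose, and the stay is to "continue until 24 hours post first AMG 176 dose for subjects on the AMG 176 QW schedule (Parts 1b, 3b, and 4"; on BIW it runs to the same interval after the second dose. Durations are tied to named parts: 1b, 3b and 4 for QW, 1a and 3a for BIW. Sites may lengthen the stay. The next note, on prophylaxis, reads "See Section 6.1.4.1 for prophylaxis requirements".

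**The body text.** Section 6.1.4.1 states that "TLS prophylaxis must be initiated in all subjects prior to all ramp-up dosing of AMG 176 and prior to all subsequent dose escalations", and explains escalation as the first dose at the targeted cohort level. It lists hospitalization, IV hydration and chemistry monitoring among the elements of prophylaxis. It adds: "Monitoring of electrolyte values is required prior to dosing anytime a dose is higher than one previously given to the subject". Sections 6.1.1 and 8.2.5.2 repeat the prophylaxis trigger and the hospitalization period.

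**Later dose changes.** Section 4.1.1 lets subjects who complete the DLT period move to a higher dose level in Part 3b or "crossover to Part 4 combinational therapy for the following treatment cycle". Section 6.1.1 has a similar rule for higher doses or different schedules. For Part 3d, Section 4.1.3 says that after day 15 "subjects will be eligible to receive the highest cleared monotherapy or combination therapy dose", subject to investigator and medical monitor agreement.

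**The concern.** TLS is an identified risk of AMG 176. Section 2.3.2.1 reports "1 subject with a fatal outcome out of 109 safety-evaluable subjects". The schedule is the part of a protocol that site staff work from day to day. If its note ends the admission after the first dose or doses while the body text calls for one at the first target-level dose, sites can handle the same dose step differently, and a site that follows the note skips an admission that the body text requires.

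The later pages raise a second problem. Escalation and crossover can fall after cycle 1, yet those pages have no line for hospitalization, prophylaxis or serial TLS tests, and nothing says that the subject goes back to a cycle 1 page. The body-text requirement then has no place in the schedule.

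**Working it through.** The plan states no figure to reproduce. The check sets the texts side by side.

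1. **Length of the first stay: no conflict.** For QW, both the note and Section 6.1.4.1 run to 24 hours after the dose. For BIW, the note ends 24 hours after the second dose. With doses on consecutive days that is 24 + 24 = 48 hours after the first dose, which is the figure in Section 6.1.4.1.

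2. **Trigger: conflict.** The note is anchored to the first dose (QW) or second dose (BIW) only. Sections 6.1.1, 6.1.4.1 and 8.2.5.2 are anchored to ramp-up dosing and to the first target-level dose. Under the ramp-up rule, week 1 of cycle 1 is given at 120 mg/m² and later doses at target. For a QW target of 180 mg/m² or more, the first target dose is therefore on day 8. The steps are 180/120 = 1.5 and 240/120 = 2. By day 8 the note's hospitalization has ended, whereas Section 6.1.4.1 has it apply again.

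3. **Note against grids: conflict.** The cycle 1 pages of Tables 1-3 and 1-5 show two hospitalization blocks, and TLS tests continue through cycle 1. The grids fit the body text; the note does not.

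4. **Coverage of the note.** It gives no duration for Part 3d, the Part 4 BIW cohorts 5a and 5b, Part 5A or Part 5B, all open to enrollment. Some have their own grid rows: Tables 1-7 and 1-8 carry hospitalization rows for Part 5B, and Table 1-5 covers Part 5A QW. The cycle 1 rows of Table 1-6 cannot be read in the available text, so nothing is inferred from them.

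5. **Cycle 2 and later.**

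| Schedule pages | TLS rows after cycle 1 |
|---|---|
| Table 1-3 (includes Part 3b) | no hospitalization, prophylaxis or TLS test row |
| Table 1-5 (Part 4 QW, Part 5A QW) | none of the three |
| Table 1-6 (Part 4 BIW, Part 5A BIW) | none of the three |
| Tables 1-7 and 1-8 (Part 5B) | TLS prophylaxis and TLS test rows present |

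   Table 1-9 says that TLS tests are done at the schedule's timepoints. Section 6.1.4.1 requires electrolyte checks before any dose higher than one already given, and dosing-day chemistry before the dose and at 2, 4, 8, 12 and 24 hours. Neither rule has a cycle limit. Pre-dose safety chemistry continues in later cycles and includes the TLS analytes (Table 11-1), but it may be drawn up to about 24 hours ahead and provides no serial post-dose samples.

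6. **Background risk.** 1/109 = 0.9%. The exact 95% lower limit is 1 − 0.975^(1/109) = 0.02%; the upper limit, solving (1 − p)^109 + 109p(1 − p)^108 = 0.025, is 5.0%. This is the overall fatal TLS rate. The protocol does not link the death to a dose escalation.

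**The case against.** The strongest reply is that the mandatory text already governs. Three sections agree on the trigger, the cycle 1 grids agree with them, and the note sits beside a pointer to Section 6.1.4.1. Escalation needs clearance by the dose-level review team and consultation with the sponsor; a Part 3d move needs investigator and medical monitor agreement. SAP Section 10 records early termination.

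Much of this stands and limits the point. It does not remove it: permission to lengthen a stay is not a requirement to admit again, a pointer does not settle a conflict with the note beside it, and nothing names the page to use after a move. Early termination lowers the urgency but leaves the text unreconciled.

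Four stronger readings are tempting, and the documents do not support them.

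- **Escalated doses go unmonitored.** The day 8 step has scheduled TLS tests, later cycles keep pre-dose chemistry, and Section 6.1.4.1 still applies. What the schedule may leave out is the admission and, after cycle 1, the serial post-dose tests.
- **Part 3d subjects face a 4-fold step (240/60).** Section 4.3 applies the 120 mg/m² ramp-up to any target of 180 mg/m² or more, across indications and schedules. On that text the steps are 120/60 = 2 and 240/120 = 2. Other passages place ramp-up in cycle 1, so its use on crossover could be clearer, but a 4-fold step is not established.
- **DLT-based dose decisions are distorted.** Sections 4.1.1 and 6.1.1 exclude DLTs after a move from dose-level decisions. On day 8 the grid sets sampling for everyone; the note governs admission.
- **Adding azacitidine at an unchanged AMG 176 dose should itself be a trigger.** Section 2.3.2.1 says the combination may raise TLS risk, but a new trigger would be a clinical preference, not a contradiction. Entry to a Part 4 cohort may already count as a first dose at that cohort's level.

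**Conclusion.** The point holds as an internal inconsistency with a safety consequence. The Table 1-9 note contradicts Sections 6.1.1, 6.1.4.1 and 8.2.5.2 and the cycle 1 grids of Tables 1-3 and 1-5. The cycle 2+ pages of Tables 1-3, 1-5 and 1-6 make no provision for escalation or crossover. Part 5B is outside the second gap.

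From planned numbers, the day 8 conflict reaches the Part 4 QW cohorts at 180 and 240 mg/m², with up to 10 subjects each (2 × 10 = 20). If Part 5A uses QW, its 24 subjects at 240 mg/m² take the same step, and the note gives them no duration. The second gap can reach the roughly 11 planned Part 3d subjects and anyone who escalates or crosses over. The documents do not say how many move.

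Two assumptions matter. Escalation after cycle 1 is taken to count as a first dose at the new cohort's target level; the explanation of escalation in Section 6.1.4.1 leaves this slightly open for hospitalization, while the electrolyte rule has no such limit. The grids are read from text with broken columns, so the finding rests on the note, the sections, the two hospitalization blocks and the absent rows, not on exact timepoints.

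**What to change.** Reconcile the Table 1-9 hospitalization note with Sections 6.1.1, 6.1.4.1 and 8.2.5.2 and with the cycle 1 grids, and make it cover every open part and schedule: Part 3d, both Part 4 schedules, Part 5A and Part 5B. State which Schedule of Activities page governs the first cycle after intra-subject escalation or crossover, including moves from Part 3d, and whether the receiving cohort's cycle 1 TLS rows apply.

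The sponsor decides when subjects are admitted, for how long and with what tests; this review takes no position on that. The cost is schedule wording. Any added inpatient days or samples would depend on the sponsor's decision and, if the body text is kept, would be ones it already requires.

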5	AML (approximately 68 subjects [24 per cohort in Part 5A, 20 in Part 5B])	Part 5A: AMG 176 in combination with azacitidine Cohorts 1 and 2: OBD Selection (QW or BIW). Part 5B: Conventional AML Dosing Schedule (5 consecutive days)	
Part 5 will begin after the completion of Part 4.
 
Part 5A:
 
Two cohorts will be enrolled to determine the combination RP2D/OBD on either a QW or BIW dosing schedule.Simon's two-stage minimax design (Simon, 1989) will be used in each cohort of Part 5A for conducting the trial.Enrollment will be restricted to subjects with persisting or recurring AML ≤ 2 prior lines of therapy. 
Part 5B (The enrollment of Part 5B will start after Part 5A is complete):
 
Two regimens will be tested, both continuing to utilize a 28-day cycle.All subjects will receive 7 days of azacitidine IV or SC daily at 75 mg/m^2 on Days 1 - 5, 8 - 9 of each 28-day cycle.Regimen 1 will administer AMG 176 at 240 mg/m^2 QD for 3 days + 4 days off followed by BIW dosing on weeks 2 and 3.Regimen 2 will administer AMG 176 at 240 mg/m^2 QD for 5 consecutive days, and then BIW on week 2 (no administration on weeks 3 and 4). Regimen 2 will only enroll if no safety issues arise after 6 subjects have enrolled in Regimen 1.Doses other than the stated 240 mg/m^2 based on emerging data.

AML = acute myeloid leukemia; BIW = twice weekly; DLRT = dose-level review team; IV = intravenous; MM = multiple myeloma; MTD = maximum tolerated dose; mTPI = modified toxicity probability interval; PD = pharmacodynamics; PK = pharmacokinetics; QD = once daily; QW = once weekly; RP2D = recommended phase 2 dose; SC = subcutaneous; US = United States

Note: Part 2 was designed to be a combination treatment for MM in a previous amendment. It was removed due to a change in AMG 176 clinical development.

Number of Subjects

Subjects with relapsed or refractory MM and subjects with relapsed or refractory AML are eligible for this study (see Section 5). It is anticipated that **approximately 219 subjects** will be enrolled in the different parts of this study.

CLOSED TO ENROLLMENT: Multiple myeloma Part 1a enrolled 36 subjects for dose escalation. Multiple myeloma Part 1b enrolled 12 subjects for dose escalation. Acute myeloid leukemia Part 3a enrolled 17 subjects for dose escalation. Part 3b enrolled 11 subjects. Acute myeloid leukemia Part 3c enrolled 4 subjects in Japan.

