Peripheral Neuropathy Assessment: For MM subjects a peripheral neuropathy assessment will be performed at screening, on treatment if clinically indicated and then at the SFU visit. A neurological examination does not need to be performed by a neurologist, but should be performed by a qualified professional with knowledge and experience performing a neurological exam.
Patient Interview Substudy – Parts 3b, 4, and 5: Approximately 10 AML subjects from Parts 3b, 4, and 5 at select sites in countries where English is the primary language will be asked to participate in a Patient Interview Substudy (one 60-minute interview). The interview will take place as soon as possible after the completion of cycle 1, excluding days on which AMG 176 is administered and days on which subjects are hospitalized.

Table 1-9. Schedule of Activities Notes and Abbreviation Definitions (continued)

AMG 176 dosing: AMG 176 will be administered IV BIW (day 1 and 2, Weeks 1, 2, and 3) or QW (day 1, Weeks 1, 2, 3, [and 4]) depending on the Part and cohort the subject is enrolled in. A ramp-up dose of 120 mg/m ² will be required if the target dose is \geq 180 mg/m ² . AMG 176 will be infused for 2 hours (\pm 5 minutes).
For Part 3d: After week 3 subjects may crossover to Part 3b or Part 4 for continued treatment if approved by the investigator and Amgen medical monitor. Subjects from Part 3d who crossover to Part 3b will not crossover (for a second time) to Part 4.
For Part 5B (conventional dosing): Dosing will be AMG 176 on 3 consecutive days the first week, and BIW on weeks 2 and 3 each cycle in the first 6 subjects (regimen 1). If this schedule is deemed safe by the DLRT, the next 6 subjects will receive AMG 176 on 5 consecutive days the first week, and BIW dosing week 2 for each cycle (Regimen 2).
Azacitidine: Azacitidine will be co-administered with AMG 176 to subjects enrolled in Parts 4 and 5. Azacitidine will be administered at a dose of 75 mg/m ² IV or SC daily for the first 7 days of a 28-day cycle.
Oral itraconazole capsules (200 mg) will be given once daily (QD) for 7 days, starting at 8 am (\pm 1 hour) on day -3 through day 4 (last dose of itraconazole will be on day 4). Itraconazole dosing on day 1 should be at approximately the same time (\pm 5 minutes) as the start of infusion of AMG 176.

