4.4 Justification for Non-investigational Product Dose

4.4.1 Azacitidine

For Parts 4 and 5A, the dose of azacitidine for the first treatment cycle, for all subjects regardless of baseline hematology laboratory values, is 75 mg/m² subcutaneously (SC) or IV, daily for the first 7 days of a 28 day cycle (as per local prescribing information).

For Part 5B, all subjects will receive 7 days of azacitidine IV or SC daily at 75 mg/m² on days 1 - 5, 8 - 9 of each 28-day cycle. Prophylactic treatment to mitigate nausea and vomiting will be administered.

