6.1.2.1 Azacitidine (Parts 4 and 5)

Description

Azacitidine is a pyrimidine nucleoside analog of cytidine. The empirical formula is C₈H₁₂N₄O₅. The molecular weight is 244 g/mol.

The mechanism of action is through hypomethylation of DNA and direct cytotoxicity. Hypomethylation may restore normal function to genes that are critical for differentiation and proliferation. The concentration of azacitidine required for maximum inhibition of DNA methylation in vitro does not cause major suppression of DNA synthesis.

Formulation

Azacitidine is a white to off-white solid. Azacitidine was found to be insoluble in acetone, ethanol, and methyl ethyl ketone; slightly soluble in ethanol/water (50/50), propylene glycol, and polyethylene glycol; sparingly soluble in water, water-saturated octanol, 5% dextrose in water, N-methyl-2-pyrrolidone, normal saline, and 5% Tween 80 in water; and soluble in dimethylsulfoxide (DMSO).

The finished product is supplied in a sterile form for reconstitution as a suspension for **SC** injection or reconstitution as a solution with further dilution for IV infusion.

Storage

Store unreconstituted vials at 25°C; excursions permitted to 15°C to 30°C (5°F to 86°F).

Accountability

Sites will be required to record and document subject compliance regarding azacitidine dosing. The quantity administered, route, start date/time, stop date/time, and lot number of azacitidine are to be recorded on each subject's CRF(s). Stop date/time is required to be recorded on each subject's CRF(s) only for IV administrations.

Azacitidine will not be supplied by Amgen for this study unless required by local regulation or in response to a regional supply shortage. In Japan, azacitidine will be supplied by Amgen for this study.

Packaging

Azacitidine is supplied as a lyophilized powder in 100 mg single use vials packaged in cartons of 1 or 2 vial(s). Vials contain 100 mg of azacitidine and 100 mg of mannitol as a sterile lyophilized powder.

Dosage, Administration, and Schedule

For Parts 4 and 5A, azacitidine will be administered at a dose of 75 mg/m² either IV or SC, as recommended in the prescribing information, daily for the first 7 days of a 28day cycle. The dose may be increased to 100 mg/m² if no beneficial effect is seen after 2 cycles and if no toxicity other than manageable nausea and vomiting has occurred.

For Part 5B, all subjects will receive 7 days of azacitidine IV or SC daily at 75 mg/m² on days 1 - 5, 8 - 9 of each 28-day cycle.

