7.3 Lost to Follow-up

A subject will be considered lost to follow-up if he or she repeatedly fails to return for scheduled visits and is unable to be contacted by the study site.

The following actions must be taken if a subject fails to return to the clinic for a required study visit:

- The site must attempt to contact the subject and reschedule the missed visit as soon as possible and counsel the subject on the importance of maintaining the assigned visit schedule and ascertain whether or not the subject wishes to and/or is able to continue in the study.
- In cases in which the subject is deemed lost to follow-up, the investigator or designee must make every effort to regain contact with the subject (where

possible, 3 telephone calls and, if necessary, a certified letter to the subject's last known mailing address or local equivalent methods). These contact attempts are to be documented in the subject's medical record.

- If the subject continues to be unreachable, he/she will be considered to have withdrawn from the study with a primary reason of lost to follow-up.
- For subjects who are lost to follow-up, the investigator can search publicly available records (where permitted) to ascertain survival status. This ensures that the data set(s) produced as an outcome of the study is/are as comprehensive as possible.

8. Study Assessments and Procedures

Study procedures and their time points are summarized in the Schedule of Activities (see Section 1.3).

As protocol waivers or exemptions are not allowed if an enrolled subject is subsequently determined to be ineligible for the study, this must be discussed with the sponsor immediately upon occurrence or awareness to determine if the subject is to continue or discontinue study treatment.

Adherence to the study design requirements, including those specified in the Schedule of Activities, is essential and required for study conduct.

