**10. Changes From Protocol-specified Analyses**

The study was terminated early. Synopsis CSR will be provided, and thus selected planned analyses will be performed. The following analyses will not be performed.

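### The Table 1-9 azacitidine note puts Part 5B on days 1-7, while the rest of the protocol and the SAP put it on days 1-5 and 8-9

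*Protocol*

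**What the plan says.** Table 1-9 holds the notes for all the Schedule of Activities tables, including Tables 1-7 and 1-8 for Part 5B. Its azacitidine note opens with "Azacitidine will be co-administered with AMG 176 to subjects enrolled in Parts 4 and 5" and then gives 75 mg/m² "IV or SC daily for the first 7 days of a 28-day cycle". Part 5 consists of Parts 5A and 5B, and the note does not separate them.

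The AMG 176 note just above it does treat Part 5B separately: "For Part 5B (conventional dosing): Dosing will be AMG 176 on 3 consecutive days the first week".

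Elsewhere the Part 5B azacitidine days are different and consistent with one another:

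- Protocol Synopsis, design table: "on Days 1 - 5, 8 - 9 of each 28-day cycle".
- Protocol Section 4.4.1: the days 1-7 schedule is confined to Parts 4 and 5A. A separate sentence begins "For Part 5B, all subjects will receive 7 days of azacitidine IV or SC daily" and gives days 1-5 and 8-9.
- Protocol Section 6.1.2.1: the same split, with Part 5B "on days 1 - 5, 8 - 9 of each 28-day cycle".
- SAP Section 3.1, design table: days 1-5 and 8-9 for Part 5B.
- Protocol Table 1-7 (Part 5B Regimen 1), cycles 2 onward: the azacitidine row is marked for D1 and D2-3, reads D4-5 in the D4-7 column, and is marked again for D8 and D9.

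**The concern.** Two dosing instructions for the same drug in the same subjects cannot both be followed. The note cannot easily be read as shorthand for Part 5A, because Table 1-9 names Part 5A wherever it means only that part: the ECG, TLS monitoring, cardiac monitoring and PK notes all do so.

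The note also belongs to the Schedule of Activities, and the opening of Protocol Section 8 states: "Adherence to the study design requirements, including those specified in the Schedule of Activities, is essential and required for study conduct". The review found no rule saying which text prevails when a schedule note and the body disagree.

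What is at stake is when azacitidine is given relative to AMG 176. Part 5B tests a schedule in which the two drugs overlap in week 2, and the safety and PK of the combination, conventional dosing included, are primary objectives in Protocol Section 3. Giving azacitidine on days 6-7 would remove that week-2 overlap.

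**Working it through.** No planned figure has to be reproduced. The check compares sets of dosing days.

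**Inputs**

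- Azacitidine in Part 5B under the main text (Synopsis, Sections 4.4.1 and 6.1.2.1, SAP Section 3.1): {1, 2, 3, 4, 5, 8, 9}.
- Azacitidine in Part 5B under the Table 1-9 note: {1, 2, 3, 4, 5, 6, 7}.
- Azacitidine dose: 75 mg/m² per administration.
- AMG 176, Regimen 1: three consecutive days in week 1, then BIW in weeks 2 and 3. Regimen 2: five consecutive days in week 1, then BIW in week 2.
- BIW means two consecutive days (Table 4-1, footnote b). Regimen 1 is therefore {1, 2, 3, 8, 9, 15, 16} and Regimen 2 is {1, 2, 3, 4, 5, 8, 9}. Each has 7 doses (3 + 2 + 2 and 5 + 2), which agrees with the 7 doses per cycle given for the conventional scheme in Section 6.1.1.

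**Difference between the two azacitidine schedules**

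Five days agree, {1, 2, 3, 4, 5}. The note replaces {8, 9} with {6, 7}, so 2 of 7 doses move. Total dose per cycle is 7 × 75 = 525 mg/m² under either version.

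**Days on which both drugs are given, per cycle**

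| | Main text | Table 1-9 note | Change |
|---|---|---|---|
| Regimen 1 | {1, 2, 3, 8, 9} = 5 | {1, 2, 3} = 3 | (3 − 5)/5 = −40% |
| Regimen 2 | {1, 2, 3, 4, 5, 8, 9} = 7 | {1, 2, 3, 4, 5} = 5 | (5 − 7)/7 = −29% |

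In Regimen 2 the main-text azacitidine days coincide exactly with the AMG 176 days. Under the note, azacitidine would be given alone on days 6-7 and AMG 176 alone on days 8-9.

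**What was not used**

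The Table 1-7 cycle 1 grid and the Table 1-8 grids are too broken in the extracted text to show which days carry azacitidine, so nothing here rests on them.

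**The case against.** The strongest reply is that the sections governing dosing settle the matter. Section 6.1.2.1 is where the azacitidine schedule is laid down, and Section 4.4.1, the Synopsis and the SAP agree with it. A Part 5B Regimen 1 site would reach Table 1-9 from Table 1-7, whose later-cycle grid already marks days 8 and 9. Azacitidine is given on site under supervision and recorded (Section 6.5). The Section 8 adherence sentence applies to that grid as much as to the note, so it gives the note no priority. All of this stands. It makes the error less likely to have an effect, but it does not make the note correct.

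Three narrower points deserve an answer:

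- **PK.** In Table 1-7 azacitidine PK sampling appears only in the unreadable cycle 1 grid, so no azacitidine sample can be shown to be lost. That is fair. AMG 176 PK in combination is also a primary objective, however, and the Table 1-7 row for it in cycles 2-4 appears to include days 8 and 9, when AMG 176 would be given without same-day azacitidine if the note were followed.
- **Percentages.** Days with both drugs is not an endpoint or an input to any decision. The percentages describe a hypothetical change in schedule, not harm.
- **Numbers.** About 20 is the planned enrollment, not a ceiling: Table 4-1, footnote d lets the study team change numbers within a Part 5 total of about 68.

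**Conclusion.** The inconsistency is real and lies in the current text. The Table 1-9 azacitidine note is the wrong one, and days 1-5 and 8-9 are clearly what was intended for Part 5B.

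Severity is low. The overlap figures above apply only if a site dosed from the note, and they rest on reading BIW as two consecutive days. No sample size, error rate, decision rule or analysis set changes. DLT incidence is a primary endpoint only for Part 4 among the azacitidine parts, and the requirement for 100% of azacitidine doses to be DLT-evaluable is also specific to Part 4.

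The number of subjects exposed is unknown and may be zero. Part 5B was to open only after Part 5A was complete, and SAP Section 10 records that "The study was terminated early". The documents do not say how many subjects entered Part 5B, or that any site followed the note.

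**What to change.** In Table 1-9, restrict the existing azacitidine note to Parts 4 and 5A. Add a sentence for Part 5B giving 75 mg/m² IV or SC daily on days 1-5 and 8-9 of each 28-day cycle, in line with Sections 4.4.1 and 6.1.2.1.

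The cost is one line of text. Design, sample size and analysis are untouched.
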